- Middle cerebral artery velocity reactivity to hypercapnia: Using non-invasive transcranial doppler ultrasound (TOC Neurovision, Multigon Industries, Inc.), blood flow velocity of the middle cerebral artery (MCA) velocity will be obtained using a 2 MHz doppler probe attached to custom headgear to maintain stable doppler signal. The basal portion of the MCA will be insonated by placing the probe over the temporal bone just above the zygomatic arch between the frontal process and front of the ear. Basal resting velocity will be obtained for 3 minuted followed by 2, 30-second breathholds separated by 1 min. Next, subjects will breathe room air through a Hans-Rudolph mouthpiece with one-way valve (to prevent rebreathing), followed by 3 stepwise increases in end-tidal CO2 (ETCO2) by adding 2%CO2, 4%CO2 and 6%CO2 fractional concentration of CO2 (FiCO2) for 3 minutes each while oxygen content is maintained at 21% and balanced by nitrogen(N). Immediately after the 9 min stepwise increase in FiCO2 trial, the subjects will breathe room air for 3 min to measure MCA velocity recovery. Cerebrovascular reactivity is calculated from the slope of the relation between increases in MCA velocity and ETCO2 in response to stepped increases in FiCO2. ETCO2 will be monitored with a Novametix NICO CO2. monitor attached to the Hans Rudolph mouthpiece, and 3 lead ECG recorded throughout testing.
- c) Brachial artery FMD (endothelium-dependent dilation, EDD) and endothelium-independent dilation. Brachial artery FMD and endothelium-independent dilation will be determined non-invasively using high-resolution ultrasonography (LOGIQ E9, GE Healthcare) as described originally by Celermajer et al. (1992) and more recently by the PI (19, 50, 60, 61). While supine, the subject's arm will be abducted and positioned comfortably on a side table and a pediatric cuff will be secured on the upper forearm (i.e., below the antecubital fold). After selecting a segment of the brachial artery ~3-6 cm above the antecubital fold with clear anterior and posterior intimal-luminal interfaces, the ultrasound probe will be clamped in place to avoid any

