Drug infusion protocol: First, baseline FBF responses to intra-brachial artery infusions of 0.9% saline will be measured for 20 min at rate of 1 ml/min. Next, FBF responses during intra-brachial artery infusions of 2 incremental doses of the endothelial agonist acetylcholine (Ach; doses 3 and 30 mcg/min) or the endothelium-independent agonist sodium nitroprusside (SNP; doses 1 and 10 mcg/min) at 1 ml/min will be performed for 6 min for each dose. Both drugs will be diluted in 0.9% saline and sequence of Ach and SNP will be randomly assigned. FBF from each drug infusion will be recorded during the 3rd to 6th minute of each dose. A washout period of 0.9% saline at 1 ml/min will be performed for 20 min or less if FBF returns to baseline sooner. Next, the effects of oxidative stress on EDD will be determined by measuring the effect of ascorbic acid (vitamin C) infusion (25 mg/min) at an infusion rate 1 ml/min for a 10 minute loading dose prior to ACh infusion, and then continuous infusion throughout incremental infusion of AcH (doses 3 and 30 mcg/min). Specifically, any difference in the FBF response to ACh and the FBF response to ACh + vitamin C can be attributed to a reduction in vascular oxidative stress. SNP is used as an NO donor to test endothelium-independent dilation to establish that any observed group differences in Ach-mediated vasodilation is due, at least in part, to stimulated endothelial NO release per se, and not impairments in smooth muscle vasodilator function to an NO donor. Note: The concentrations selected for each of these agents have been shown to elicit changes in FBF without affecting systemic hemodynamics (i.e., no changes in heart rate or blood pressure).

b) Microneurography. Direct intra-neural recordings of sympathetic activity to skeletal muscle will be obtained using microneurography, as previously described. A tungsten micro electrode (200  $\mu$ m diameter shaft; 1-5  $\mu$ m uninsulated tip) is inserted into the peroneal nerve posterior to the head of the fibula. Well-validated criteria are used to

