### XI. Data Analysis

### XI.1 Describe the analysis methods you will use, including, if applicable, the variables you will analyze

Statistical analyses. To determine if differences in outcomes are present at baseline between obese pre-diabetic vs. non-pre-diabetic groups, an independent two-sample t-test will be performed. To determine if baseline (pre-intervention) differences exist between salsalate and placebo prediabetic groups after randomization, independent two-sample t-tests will be performed. To test the main hypotheses, a repeated measures ANOVA will be performed in which treatment (salsalate vs. placebo) is the between-subjects factor, and time (pre- vs. post-intervention outcomes) is the within-subjects factor for the primary dependent variables. The critical test for the dependent variable will be the interaction between the within-subjects and betweensubjects factors. Tests for mean contrasts will be used to compare variables of interest pre vs. post Salsalate or placebo. Based on a previous study, we expect small reductions in fasting glucose, triglycerides, LDL cholesterol and possibly systolic blood pressure after Salsalate treatment. Covariates (e.g., variables that change after Salsalate) will be included into the mixed model. Bivariate pearson correlation analysis will be performed on the change in each dependent variable and aforementioned selected covariates after Salsalate.

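### Nitroprusside is infused to attribute acetylcholine differences to the endothelium, but XI.1 plans no comparison of the two agonists, and a non-significant nitroprusside test is weak evidence at this sample size

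*Combined protocol and SAP*

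**What the plan says.** **Purpose of SNP.** VII.E.6 (Experimental Methods for Visit 4, drug infusion protocol) measures forearm blood flow (FBF) during two doses of ACh (3 and 30 mcg/min) and two of SNP (1 and 10 mcg/min). SNP is there to "establish that any observed group differences in Ach-mediated vasodilation is due, at least in part, to stimulated endothelial NO release per se". The rival explanation that it is meant to rule out is altered responsiveness of the smooth muscle itself.

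**Analysis.** XI.1 describes one main model, in which "treatment (salsalate vs. placebo) is the between-subjects factor, and time (pre- vs. post-intervention outcomes) is the within-subjects factor". It adds: "The critical test for the dependent variable will be the interaction between the within-subjects and betweensubjects factors". The follow-up is: "Tests for mean contrasts will be used to compare variables of interest pre vs. post Salsalate or placebo". On adjustment it says: "Covariates (e.g., variables that change after Salsalate) will be included into the mixed model". The prediabetic v non-prediabetic comparison at baseline is a two-sample t-test. XI.1 does not mention FBF, ACh, SNP or dose. VII.B.11 says that no separate written protocol will be submitted.

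**Size.** XI.2 assigns 20 subjects to salsalate and 10 to placebo and expects 15-20% attrition. It is based on carotid-femoral PWV (d = 1.06) and flow-mediated dilation, FMD (d = 1.2). It gives no figure for FBF.

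**The concern.** To attribute a difference in ACh dilation to the endothelium, the effect on ACh must be set against the effect on SNP. The planned model has no agonist factor, and no ACh-minus-SNP endpoint or ratio is defined. No margin is given for calling the SNP response unchanged. An analyst who follows XI.1 gets one p-value for ACh and another for SNP, and must reach the mechanistic conclusion by comparing them. One result being significant and the other not does not show that the two effects differ.

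At stake is the microvascular interpretation under Aim 1. A general change in vasodilator response, equal for both agonists, could be reported as an endothelial effect. The forearm data come from brachial artery catheterisation at two visits, so the analysis should be able to answer the question for which SNP was included.

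**Working it through.** **1. The plan's own figures.** For a two-sample t-test, two-sided alpha 0.05 (sidedness is not stated) and 80% power, d = 1.06 needs 15 per group against the stated 16, and d = 1.2 needs 12 against the stated 12. With 20% attrition, 16/0.80 = 20, which matches the salsalate arm. The figures reproduce closely, but neither concerns FBF.

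**2. Inputs.** From XI.2: 20 v 10 randomised, and at 20% attrition 20 × 0.80 = 16 and 10 × 0.80 = 8 completers. Assumed: standardised effects of 0.6 to 1.06 SD on the change score, and a correlation of 0.3 to 0.7 between the ACh and SNP changes.

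**3. Power of one SNP test.** The treatment-by-time interaction with two time points equals a t-test on change scores. The noncentrality is d × √(n1·n2/(n1+n2)), with n1+n2−2 degrees of freedom.

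| Completers | √(n1·n2/(n1+n2)) | Power, 0.8 SD | Power, 1.06 SD |
|---|---|---|---|
| 16 v 8 | √(128/24) = 2.31 | 42% | 65% |
| 20 v 10 | √(200/30) = 2.58 | 51% | 75% |

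A real SNP effect of 0.8 SD would be missed in 49% to 58% of trials, and one of 1.06 SD in 25% to 35%.

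**4. Equal true effect on both agonists.** Simulation at 16 v 8, correlation 0.5, 40,000 trials per setting:

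| Effect | ACh significant and SNP not, all trials | SNP not significant, given ACh significant |
|---|---|---|
| 0.6 SD | 14% | 52% |
| 0.8 SD | 17% | 40% |
| 1.0 SD | 16% | 28% |
| 1.06 SD | 16% | 24% |

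Over correlations 0.3-0.7 the ranges are about 10-20% of all trials and 19-62% of those with ACh significant. With no attrition (20 v 10, correlation 0.5) the pattern appears in 17% of all trials at 0.8 SD and 13% at 1.06 SD.

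**5. Direct contrast.** Under the same assumptions and with equal SDs, a two-sided test of ACh change minus SNP change falsely favours ACh in 2.5% of trials. That figure depends on the scale. If the ACh change has 1.5 times the SD of the SNP change, with the same standardised effect on each, the raw difference falsely favours ACh in 10% (0.8 SD) to 14% (1.06 SD) of trials. At twice the SD it is 17% to 27%. The scale must therefore be chosen in advance.

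**6. What the contrast costs in power.** In SD units its variance is 2(1−ρ). If the effect is on ACh only (1.06 SD, 16 v 8), its standardised size is 1.06/√(2(1−ρ)): 0.90, 1.06 and 1.37 at ρ = 0.3, 0.5 and 0.7. Power to find it is about 51%, 65% and 86%, against 65% for ACh tested alone.

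**7. Which ACh response matches SNP.** The drug infusion protocol describes SNP alone. The Visit 4 list in VII.E.6 (item c) and the ascorbic acid entry in V.8 describe SNP with vitamin C. If SNP is given only with vitamin C, a contrast with ACh alone mixes the agonist effect with the vitamin C effect.

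**The case against.** **The plan states no such rule.** A reader might infer that it commits to claiming an endothelial effect when ACh is significant and SNP is not. The documents do not support that reading: XI.1 gives no interpretation rule for any of the pharmacological tests. What stands is narrower. Separate tests are the only route that XI.1 leaves to the claim.

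**The stated aim is modest and broader than the treatment effect.** It speaks of group differences and says at least in part. It therefore does not promise to exclude smooth muscle, and it fits the prediabetic v non-prediabetic baseline comparison (30 v 10) as well as salsalate v placebo. Both points are fair. But an equal effect on both agonists would not support even a partial endothelial attribution, and the same gap exists at baseline, where only a t-test is planned.

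**The covariate sentence might admit the SNP response.** It does not name it, and adjusting for a variable measured after treatment is not a comparison of agonists.

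**The same flaw might be inferred for FMD v nitroglycerin.** The heading "Brachial artery FMD (endothelium-dependent dilation, EDD) and endothelium-independent dilation" shows that both are measured, but that section makes no matching attribution claim. The extension is by analogy only and is not needed here.

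**It is a pilot, and FBF is not the primary outcome.** This is correct and limits the weight of the point. PWV is unaffected.

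**Conclusion.** The point holds in this form: the protocol gives SNP an attributional purpose, and XI.1 contains no analysis that serves it. A non-significant SNP test could not fill the gap, since its power is 42-65% at 16 v 8 and 51-75% at 20 v 10 for effects of 0.8-1.06 SD. Under equal standardised effects the misleading pattern would appear in about 10-20% of all trials at 16 v 8. The larger range, 19-62%, applies only to trials in which ACh is already significant.

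All forearm inputs (effect, SD, correlation) are assumptions, so these figures show the order of size and are not predictions. The consequence is confined to a secondary, mechanistic conclusion under Aim 1. The change is worth making because it is cheap, but the trial's main result does not depend on it.

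**What to change.** 1. **Reconcile the infusion passages first**: the drug infusion protocol (SNP alone) against the Visit 4 list and the V.8 ascorbic acid entry (SNP with vitamin C). Then define the contrast so that ACh and SNP are compared under the same vitamin C condition.
2. **Add one contrast to XI.1.** For each subject and visit, express FBF during each drug as a log ratio to its preceding saline baseline and average over the two doses. Run the planned treatment-by-time test on the within-subject ACh-minus-SNP difference, on this one prespecified scale.
3. **State the rule.** Report the estimate and 95% CI as exploratory. Claim an endothelium-specific effect only if the CI excludes zero in favour of ACh.
4. **Always report the SNP effect with its 95% CI**, and do not read p > 0.05 as preserved smooth-muscle function.
5. **Use the same contrast** for the prediabetic v non-prediabetic comparison at baseline.

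**Cost.** Once step 1 is settled, the rest is analysis wording and needs no new measurements. The result depends on the chosen scale: the log ratio defines an equal effect as the same proportionate change in flow, which is a judgement. The specific claim may also be made less often if the ACh-SNP correlation is low (power 51% at a correlation of 0.3 in the example above).

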**Hypothesis 1:** Chronic inflammation inhibition will improve microvascular and large elastic artery function in obese adults with prediabetes.

**Aim 2:** To measure muscle sympathetic nervous system activity (MSNA) and baroreflex sensitivity in obese prediabetic adults before and after 1 month of salsalate or placebo.

**Hypothesis 2:** Chronic inflammation inhibition will decrease MSNA and improve baroreflex sensitivity in obese adults with prediabetes.

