#### Visit 1 (3.5 hours): Consent and Screening

- a. Explanation of the study; reading and signing of written informed consent b. If subject consents but requires a 2-week washout for aspirin, salicylate, NSAID, vitamin, supplements, they will be scheduled to complete the Visit 1 in 2 weeks. If subject consents and no washout is needed, screening tests will be performed same day to determine eligibility by the following:
- i. Research staff will obtain resting vitals (blood pressure, heart rate)
- ii. Research staff will obtain anthropometrics including weight, height, waist and hip circumference with tape measure.
- iii. Research staff will obtain resting 12-lead ECG
- iv. Subject will fill out the Demographics and Health History survey, and the Modified Activity Questionnaire (MAQ)
- v. Research nurse or trained staff will obtain venous blood draw using butterfly needle for UIHC pathology labs:
- Creatinine, Lipid panel, TSH(4.5 ml blood- 1 light green PST tube)
- Complete blood count(4.5 ml blood- 1 lavender tube)
- Subject will undergo oral glucose tolerance test (OGTT): Subject will consume a beverage containing 75 grams of glucose. Blood samples will be collected at timed intervals of baseline, 1 hour and 2 hours after consuming beverage for glucose and insulin. Total blood collected for insulin and glucose for OGTT: 13.5 ml blood (4.5ml x 3 PST tubes).
- TOTAL blood collected for Visit 1: 22.5 ml (1.5 Tablespoons)

- Visit 2 (2 hours): Dietary food record, cerebral blood flow velocity
- a. Meet with CRU bionutritionist for instruction on 3-day dietary record to return on visit 3
- b. Middle cerebral artery blood flow velocity using transcranial dopper during the following protocol to measure cerebral vasoreactivity to hypercapnia:
- -After 3 min of normal breathing, subjects will perform 2, 30 second breathholds sparated by 3 min.
- -Next, After 3 min of room air breathing, 3 min of breathin 2%CO2, 3 min of breathing 4%CO2 (balanced with 21%O2 and N) will be performed followed by 3 min of room air breathing.
- c. Subject will be instrumented with 24 hour blood pressure monitor to wear home for 24 hours. Subject will return it to the investigators when come in for Visit 3. There is no long term follow up.
- Visit 3 (3 hours): 1st Baseline experimental visit (Blood, Endothelial cells, FMD, PWV and Retina scan)
- a. Subject arrives at the CRU between 7-10 am after overnight 8 hour fast

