determine that a neurogram represents sympathetic activity to muscle or skin: We have used this technique safely in over 2000 studies since February 1984 and it is well tolerated and reproducible. The mental stress test is a non-baroreflex mediated sympathoexcitatory stimulus used to test sympathetic responsiveness. This test requires that each subject to subtract continuously the number 7 from a 3-digit number as quickly and as accurately as possible for 3 minutes. During the test, the participants are intentionally frustrated by being asked to calculate faster and by being corrected in case of wrong answers. This stimulus has little effect on muscle SNA and increases forearm blood flow.

c) 24-hour ambulatory blood pressure variability and baroreflex sensitivity. Twenty-four hour systolic blood pressure will be recorded using standard ambulatory blood pressure assessment (90207-IQ, Spacelabs Healthcare, Inc)and 24 hour blood pressure variability determined from the standard deviation of systolic and mean blood pressure recordings. Baroreflex sensitivity will be determined by recording blood pressure and heart rate continuously for 15 minutes during visit 3 and 6 using via beat-to-to beat finger blood pressure (Finometer MIDI, Finopress Medical Systems) and calculated using the sequence technique.

Microneurography training controls:

We will recruit 20 additional healthy control volunteers who will have microneurography performed on them by [name]. The training will be provided by [name] and [name], both of whom are highly trained in the technique and will provide close oversight in the training. The 20 volunteers will sign and separate consent form (see attached) and will be compensated \$25.

- VII.E.7 Will you attempt to recontact subjects who are lost to follow-up?

  No followup is not required in this study
- VII.E.9 Will subjects be provided any compensation for participating in this study?

  Yes
  - VII.E.10 Cash

No

VII.E.11 Gift Card

No

VII.E.12 Check

Yes

VII.E.13 Who will be providing the research compensation check to the subject?

Accounting Services directly via the e-Voucher system

VII.E.16 Other

No

- VII.E.19 Describe the compensation plan including
  - · Compensation amount and type per visit
  - Total compensation
  - Pro-rating for early withdrawal from study

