### XI.2 Provide the rationale or power analysis to support the number of subjects proposed to complete this study.

Sample size calculations. Sample sizes were calculated based on 80% power at an alpha level of 0.05. Estimated effect sizes for Aim 1 were used for final sample size calculation for obese prediabetic subjects because carotid-femoral PWV is the primary outcome and has the smallest effect size (d) in pilot data of 4 days before vs. after Salsalate. A sample size of 16 subjects per group was determined based on the d of 1.06, based on mean difference in carotid-femoral PWV (-1.0  $\pm$  1.0 m/sec) after Salsalate vs. Placebo.

With a conservative estimated attrition rate of 15-20% and the 2:1 randomization, a total of 20 subjects will be assigned to the Salsalate group, and 10 subjects to the placebo group was determined to be required for the study (total sample size=30). A

sample size of 12 for Aim 2 (FMD) was determined from d of 1.2 for a mean difference in FMD of  $\pm$  2.2 after 4 days Salsalate vs placebo based on previously published work by the PI (19). Because the effect sizes for Aim 1 and 2 are based on preliminary data of 4 days of Salsalate treatment and our proposed study is 4 weeks, we predict that the actual effect sizes will be slight higher because of the longer duration of treatment. Therefore, the proposed study will help determine actual effect sizes for chronic Salsalate therapy for a future larger randomized clinical trial.

A total of 10 obese non-prediabetic control subjects will be recruited to established differences in main outcomes at baseline but will NOT undergo randomization or salsalate/placebo treatment period.

Therefore, total sample size to be enrolled is 40.

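### The plain 24-hour SD of blood pressure mixes the day-night difference with within-period spread, so it cannot tell a change in the night-time dip from a change in variability

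*Combined protocol and SAP*

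**What the plan says.** In section VII.E.6, item c) of the Visit 4 methods says: "Twenty-four hour systolic blood pressure will be recorded using standard ambulatory blood pressure assessment". It then defines the outcome as "24 hour blood pressure variability determined from the standard deviation of systolic and mean blood pressure recordings". No reading interval, day and night windows, weighting, removal of the daily trend or separate analysis of the dip is given there or elsewhere.

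The visit schedule in the same section fits the monitor at Visit 2 (item c) and again at Visit 6 (item e): "Subject will be instrumented with 24 hour blood pressure monitor to wear home for 24 hours". Each recording therefore covers both waking and sleep, once before treatment and once at its end. The non-prediabetic controls attend Visit 2, so they contribute a baseline recording.

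Section XI.1 plans two-sample t-tests of baseline outcomes between the prediabetic and non-prediabetic groups. For the treatment comparison it plans a repeated measures ANOVA and states: "The critical test for the dependent variable will be the interaction between the within-subjects and betweensubjects factors". It does not mention blood pressure variability by name. On pressure level, it says: "we expect small reductions in fasting glucose, triglycerides, LDL cholesterol and possibly systolic blood pressure after Salsalate treatment".

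**The concern.** A standard deviation taken over all readings in 24 hours has two sources: the spread of readings within the day and within the night, and the gap between the day mean and the night mean. The second is a feature of the daily pressure profile. The definition in VII.E.6 adds the two together and provides nothing to take them apart again.

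Two planned comparisons are exposed. In the randomised comparison, if salsalate lowered pressure by a different amount by day than by night, the SD would move even if within-period spread stayed the same. In the baseline comparison with non-prediabetic controls there is no randomisation, so any group difference in dip passes straight into the SD. In either case the result could be described as a difference in variability when it is a difference in dip. A real change in within-period spread could also be masked by a dip change in the other direction.

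**Working it through.** The plan states no figure for this outcome, so there is nothing of its own to reproduce. The check is a variance decomposition with assumed inputs.

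**Inputs**
- From the documents: the outcome is the SD of the 24-hour recordings, with no day/night split (VII.E.6, item c); the recording spans waking and sleep (VII.E.6, Visits 2 and 6).
- Assumed, because the documents give none: daytime share of readings p = 2/3; within-period SD w = 10 mmHg (range 8 to 12); day-night difference D = 10 to 20 mmHg.

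**Formula**

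SD24² = p·SDday² + (1-p)·SDnight² + p(1-p)·D²

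With equal within-period SDs this is SD24² = w² + p(1-p)·D². At p = 2/3 the factor p(1-p) is 2/9.

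**Main example (w = 10, p = 2/3)**
- D = 15: √(100 + 2/9 × 225) = √150 = 12.25 mmHg. The dip supplies 50/150, one third of the variance.
- D = 10: √(100 + 2/9 × 100) = √122.2 = 11.06 mmHg.
- Difference: 12.25 - 11.06 = 1.19 mmHg, with within-period spread unchanged.

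**Range**
- The same 15-versus-10 contrast at w = 8: √114 - √86.2 = 10.68 - 9.29 = 1.39 mmHg. At w = 12: √194 - √166.2 = 13.93 - 12.89 = 1.04 mmHg.
- Share of the 24-hour variance due to the dip: smallest at D = 10, w = 12 (22.2/166.2 = 13%), largest at D = 20, w = 8 (88.9/152.9 = 58%).
- Daytime share: at w = 10 and D = 15, moving p from 2/3 to 3/4 changes the SD from 12.25 to √(100 + 0.1875 × 225) = 11.92 mmHg, so the mix of day and night readings also matters.

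**Unequal day and night SDs, and the alternative measure**

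Take SDday = 10, SDnight = 8, p = 2/3. The within-period variance is 2/3 × 100 + 1/3 × 64 = 88. The duration-weighted SD is 2/3 × 10 + 1/3 × 8 = 9.33.

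| D (mmHg) | Plain 24-hour SD | Duration-weighted SD |
|---|---|---|
| 0 | 9.38 | 9.33 |
| 10 | 10.50 | 9.33 |
| 15 | 11.75 | 9.33 |
| 20 | 13.30 | 9.33 |

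A simulation of 20,000 profiles with 48 day and 24 night readings gave plain SDs of 10.47, 11.75 and 13.32 at D = 10, 15 and 20, against weighted SDs of 9.26 to 9.27.

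**What does not move the SD**

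Subtracting the same amount from every reading leaves SDday, SDnight and D unchanged, so SD24 is unchanged. A fall in pressure matters here only if it differs between day and night.

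**The case against.** The strongest reply is that label and calculation agree: the protocol calls the outcome 24-hour variability and takes the SD over 24 hours. Nowhere does it claim to isolate within-period variability. That is fair. The plain SD is a legitimate description, which is why it should be kept. What stands is that it has two components, and a reader of the result could not tell which one had changed.

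Second, a reader might infer from XI.1 that salsalate is expected to lower systolic pressure and that the SD will therefore be biased. The documents do not support this. XI.1 offers a systolic fall only as a possibility, a uniform fall leaves the SD alone, and no section says that salsalate changes the dip.

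Third, the trial is randomised and double-blind with a placebo arm, and the interaction is the critical test. Dip changes common to both arms cancel there in expectation, as do shifts in the mix of readings that are similar in both arms. This protection is real, but it does not extend to a treatment effect on the dip or to the non-randomised baseline comparison. Chance differences in dip also add noise with 20 and 10 subjects.

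Fourth, a reader might take the point as a threat to Aim 2. It is not. The hypothesis reads "Chronic inflammation inhibition will decrease MSNA and improve baroreflex sensitivity in obese adults with prediabetes" and does not name blood pressure variability. Baroreflex sensitivity comes from a separate 15-minute beat-to-beat recording and is unaffected. Section XI.2 states that "carotid-femoral PWV is the primary outcome", so the sample size is untouched as well.

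Finally, the sizes shown rest wholly on assumed inputs. The 13% to 58% range is the dip's share of variance, not a bias in a treatment effect, and the example needs the dip to differ by 5 mmHg.

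**Conclusion.** The point holds as a limit on what the planned measure can show. That the SD contains p(1-p)D² is an identity and needs no assumption beyond a recording that spans day and night. The size does need assumptions: with p = 2/3 and a within-period SD of 10 mmHg, a dip of 15 rather than 10 mmHg changes the SD by about 1.2 mmHg (1.0 to 1.4 for within-period SDs of 12 down to 8) with no change in within-period variability.

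The documents do not establish that such a dip change or group difference will occur, or that it would be misreported; they establish only that the planned measure could not distinguish it. The outcome is a supporting one, named in no aim or hypothesis, so this is a low-priority improvement and not a flaw in the main analysis.

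**What to change.** In VII.E.6, item c):
- define fixed clock-time day and night windows in advance, the same for all subjects and both recordings;
- compute the SD within each window, for systolic and for mean pressure, from the recordings already planned;
- use the mean of the two SDs, weighted by window duration, as the variability measure;
- report the day mean minus the night mean as a separate variable;
- keep the plain 24-hour SD as a descriptive figure.

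The cost is a sentence or two of protocol text and a few lines of analysis. No new visit, device or subject is needed, assuming that the stored readings carry clock times. The sample size does not change.

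The small downside is that fixed windows only approximate waking and sleep. The list of questionnaires and written assessments in VII.E.4 includes no sleep diary, so windows based on each subject's own sleep times would need extra data. Readings that fall on the wrong side of a boundary will leave a little of the dip inside the weighted SD.
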